- Response rates: Response rates will be measured as the proportion of patients with the best response, complete response (CR) or partial response (PR), as defined by RECIST 1.1 Criteria and a 95% confidence interval.
- Adverse events: All adverse events will be listed by type and grade.

- **Biomarkers of efficacy of VOR/HCQ and RGF:** The significance of variation in biomarkers with treatment will be assessed with linear models with and without adjustment for age, sex, race and the baseline tumor K-RAS status (mutated, wild type). The dependent variables will be log transformed (base 2) if necessary. The relation between treatment efficacy, as measured by PFS-1, and biomarkers will be assessed with proportional hazards models in terms of treatment, the biomarker, the biomarker by treatment interaction, age, sex, race, and baseline tumor K-RAS status (mutated, wild type). Significant effects will be described and illustrated, as appropriate, with Kaplan Meier plots by strata determined by biomarker level and treatment group, for example.

Sample size justification: Historically, the mPFS for previously treated mCRC patients treated with RGF is 1.9 mos. We predict VOR/HCQ will improve mPFS to 3.8 months. We expect 5% lost to follow-up. Assuming a 36-month accrual period with 1 year for follow up, 36 subjects per group are necessary to obtain 80% power. With 5% lost to follow-up the sample size required per group is 38 ($=36/0.95$), therefore, the total required sample size is 76 subjects. As a result, the target accrual rate is 2-4 patients/month to achieve a target accrual at 36 months with an additional 12-month follow-up.

Funding, Regulatory, and Feasibility Issues: The study will be funded by a CPRIT grant. We previously obtained VOR through Merck Pharmaceuticals for both our phase 1 and 2 studies. However, with VOR coming off patent in late 2014, the purchase of generic VOR at low cost is likely. HCQ is already being purchased at low market cost ($<\$50/\text{month per patient}$). Thus, the VOR/HCQ combination provides a cost-effective study drug combination. We have a large referral volume of mCRC patients to our institution for consideration of clinical studies, therefore we do not expect problems with enrollment since we currently enroll 3-4 refractory mCRC patients/month onto phase I clinical trials.

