2.6. Correlative Studies

2.6.1 Correlative Studies of autophagy inhibition in relation to efficacy.

Furthermore, preliminary data at our institution has shown that the induction of biomarkers of autophagy cathepsin D (CTSD) and CDKN1A correlate both in PBMCs and patient's primary tumor using RT-PCR and electron microscopy (EM) (Fig 2 A-D) with efficacy of VOR/HCQ(6). We also observed increases in SQSTM1/p62 levels in PBMCs in patients treated with VOR/HCQ. (6) In addition, expression of high-mobility group box 1 (HMGB1) increases with autophagy in CRC, and HMGB1 acts upon binding to RAGE ("receptor for advanced glucated

end products") (7, 8). Also, LDH has been associated with necrotic cell death due to autophagy, which should decrease with autophagy inhibition (58). *Thus, we hypothesize that with VOR/HCQ, and thus autophagy inhibition, CTSD, CDKN1A, and SQSTM1/p62 will increase, and that HMGB and RAGE levels will decrease.* The change in expression levels of these various cellular proteins appears to be correlated with clinical efficacy.

Therefore, we suggest prospectively incorporating the identification of such predictive biomarkers in this study and the assessment of such biomarkers relative to the efficacy of agents evaluated. Establishing a predictive biomarker associated with clinical sensitivity to autophagy inhibitors is necessary for the optimal development of this class of drugs for cancer therapy. In addition, delineation of patients who would benefit from autophagy inhibition should reduce unnecessary costs and toxicities.

In addition, HDAC has been well-recognized as potential targets for the treatment of numerous aging-related disorders (9) such as cancer (10). Therefore, we plan to evaluate the potential role of biomarkers of aging with the combination of HCQ plus VOR.

2.6.2 Correlative Studies of anti-angiogenic inhibition in relation to efficacy.

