- Biomarkers of efficacy of VOR/HCQ and RGF: We will obtain blood samples for plasma and PBMCs before start of treatment, prior to cycle 2, and off study treatment.

5.8 Biomarker Analysis.

Five blood samples will be collected during the timepoints listed above:

- Baseline (within 14 days of starting Cycle 1)
- Pre-Cycle 2
- Off Study Treatment

Blood samples will be collected in three tubes:

- Two - 10-ml EDTA tubes for plasma
- Three - 8 mL Vacutainer CPT tube for PBMCs

The blood samples will be processed, and stored at Pharmacokinetic Sampling Department (PSD), Institute of Drug Development, at the Cancer Therapy and Research Center.

Preparation of Plasma samples:

- 1) Collect 20 mL of whole venous blood into 2- 10 mL EDTA tubes
- 2) Centrifuge tubes at 2000 g for 15 minutes, at 4 C, to separate the cells from the Plasma.
- 3) Prepare the labels for the cryovials. The label for each tube should be written in black water fast ink.
- 4) Carefully transfer the top layer of the plasma from the EDTA tubes being careful not to disturb the Buffy Coat (white layer just below the plasma). Transfer up to 2 mL aliquots of plasma from the blood collection tubes into each of the 6 – 3.6 ml skirted bottom externally threaded cryovials.
- 5) Transfer the white thick layer above the red blood cell pellet from the blood collection tube into 2 – 2 ml cryovials.
- 6) Affix each label lengthwise to its corresponding tube and secure each label with a strip of clear plastic tape wrapped completely around the tube to ensure the label remains affixed to the tube during the freezing storage.
- 7) Immediately place the labeled tubes of plasma and buffy coat in an upright position in a 20°C freezer.
- 8) **Within 12 hours, transfer samples to -70°C freezer for long-term storage.**

Preparation of PBMC samples:

- Draw 8 mL of whole venous blood directly into each 8 mL Vacutainer CPT tubes and gently invert each tube 8 times.
- After inverting the tubes, centrifuge both tubes at room temperature at 1500-1 800 g (2800 rpm) for 20 minutes. NOTE: Centrifuge must be capable of generating at least 1500 RCF at the tube bottom.
- Draw off the clear plasma layer and discard, leaving behind cloudy PBMC layer lying just above the gel barrier.
- Transfer the PBMC layer into one 14 mL polypropylene centrifuge tubes.
- Add 10 mL of PBS-DEPC (at room temperature) to each tube and invert 3 to 4 times.
- Centrifuge at room temperature at 300 g (-1200 rpm) for 5 minutes.

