- Biomarkers of efficacy of VOR/HCQ and RGF: Biomarkers will be graphically displayed to demonstrate patterns across time and group and to identify the need for transformations and potential outliers. The significance of variation in biomarkers with treatment will be assessed with linear models with and without adjustment for age, sex, race and the baseline tumor KRAS status (mutated, wild type). The dependent variables will be log transformed (base 2) if necessary. The relation between treatment efficacy, as measured by PFS-1, and biomarkers will be assessed with proportional hazards models in terms of treatment, the biomarker, the biomarker by treatment interaction, age, sex, race, and baseline tumor K-RAS status (mutated, wild type). Significant effects will be described and illustrated, as appropriate, with Kaplan Meier plots by strata determined by biomarker level and treatment group, for example.

Sample size justification: Historically, the mPFS for previously treated mCRC patients treated with RGF is 1.9 mos. We predict VOR/HCQ will improve mPFS to 3.8 months. We expect 5% lost to follow-up. Assuming a 36-month accrual period with 1 year for follow up, 36 subjects per group are necessary to obtain 80% power. With 5% lost to follow-up the sample size required per group is 38 ($=36/0.95$), therefore, the total required sample size is 76 subjects. As a result, the target accrual rate is 3-4 patients/month to achieve a target accrual at 36 months with an additional 12-month follow-up.

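### The biomarker treatment comparison omits the patient's own pre-treatment biomarker value as a covariate and leaves the outcome and visit undefined, giving up power that costs nothing to recover

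*Combined protocol and SAP*

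**What the plan says.** Section 10.0, in the entry on biomarkers of efficacy, plans two analyses. The second relates PFS-1 to the biomarkers with proportional hazards models and is not at issue here. The first asks whether biomarkers differ with treatment, and this is to be "assessed with linear models with and without adjustment for age, sex, race and the baseline tumor KRAS status (mutated, wild type". The statistical methods in the synopsis say the same: "assessed with linear models with and without adjustment for age, sex, race and the baseline tumor K-RAS status".

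On the outcome, Section 10.0 adds only "The dependent variables will be log transformed (base 2) if necessary". It does not say whether that variable is the value at one visit, a change from baseline, or all visits together. Time appears only in a descriptive step: "Biomarkers will be graphically displayed to demonstrate patterns across time and group".

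Section 5.7 sets out the sampling: "We will obtain blood samples for plasma and PBMCs before start of treatment, prior to cycle 2, and off study treatment". Section 5.8 gives the window for the first draw, "Baseline (within 14 days of starting Cycle 1", and the Section 6.0 calendar schedules the same three draws. Section 2.6.1 states the hypothesis as movement under VOR/HCQ: "CTSD, CDKN1A, and SQSTM1/p62 will increase, and that HMGB and RAGE levels will decrease".

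**The concern.** In a randomised comparison of a continuous laboratory marker, the patient's own pre-treatment value is usually the strongest available predictor of the later value. Putting it in the model removes between-patient variation from the treatment contrast. The plan names four other covariates and leaves this one out, although the sample is to be taken and the hypothesis is about change under treatment. The trial is sized for PFS-1, not for biomarkers, so this objective has little power to spare.

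There is also a gap in specification. With three draws per patient, the outcome, the visit and the handling of within-patient correlation all have to be stated before the model is defined. As written, the analyst could choose among several quite different analyses after seeing the data.

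**Working it through.** **The plan's own figure.** The documents give no power for the biomarker analysis. The number per arm comes from PFS-1. Medians of 1.9 and 3.8 months give a hazard ratio of 1.9/3.8 = 0.5. Freedman's formula with two-sided 5% (assumed) and 80% power gives (1.960 + 0.842)² × (1.5/0.5)² ≈ 70.6, so 71 events. With exponential PFS, 36 months' accrual and 12 months' follow-up, the mean event probability is 0.991. Then 71/0.991/2 ≈ 35.8, so 36 per group, and 36/0.95 = 37.9, so 38. The plan's 36 and 38 are reproduced.

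**Assumed inputs.** The documents give no biomarker SD, effect size, within-patient correlation or test level. I take SD = 1 at each visit, an arm difference of 0.5 SD at pre-cycle 2, correlation ρ of 0.3, 0.5 or 0.7 between baseline and pre-cycle 2, and two-sided 5%.

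**Power for one post-baseline visit.** The residual variance for the treatment contrast is:

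- raw later value: 1
- change from baseline: 2(1 − ρ)
- later value adjusted for baseline: 1 − ρ²

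The noncentrality is 0.5/(s√(2/n)), where s is the square root of that variance. Power comes from the noncentral t distribution with 2n − 2 degrees of freedom, or 2n − 3 with the baseline covariate. For n = 38 and the raw value, the noncentrality is 0.5/√(2/38) = 2.18 and power is 58%. Other covariates are left out of this sum.

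| ρ | Raw value | Change score | Baseline-adjusted | Reduction in residual variance (ρ²) |
|---|---|---|---|---|
| 0.3 | 58% | 44% | 62% | 9% |
| 0.5 | 58% | 58% | 70% | 25% |
| 0.7 | 58% | 79% | 85% | 49% |

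For the same power, the unadjusted analysis needs about 1/(1− ρ²) times as many patients: 1.10, 1.33 or 1.96. If only 30 per arm supplied both draws, the raw value would give 48%, and baseline adjustment 51%, 59% or 76%.

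**Type I error under different readings of the plan.** If k draws per patient are entered as independent and the treatment main effect is tested, the true variance of the contrast is 1 + (k − 1)ρ times what the model assumes. The true error rate is then about 2[1 − Φ(1.96/√(1 + (k − 1)ρ))]. For k = 3 and ρ = 0.5 the factor is 2.0, 1.96/√2 = 1.39, and the rate is 16.6%. Simulation used 36 per group and 4,000 null runs per correlation.

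| Reading | ρ = 0.3 | ρ = 0.5 | ρ = 0.7 |
|---|---|---|---|
| One visit, no baseline (simulated) | 5.1% | 5.3% | 5.2% |
| One visit, baseline-adjusted (simulated) | 4.9% | 5.4% | 5.1% |
| Two post-baseline draws pooled, formula (simulated) | 8.6% (9.0%) | 11.0% (11.2%) | 13.3% (13.8%) |
| All three draws pooled, formula (simulated) | 12.1% (12.5%) | 16.6% (16.1%) | 20.6% (21.5%) |
| Treatment-by-time contrast, baseline and pre-cycle 2 taken as independent, formula (simulated) | 1.9% (1.7%) | 0.6% (0.8%) | 0.03% (0.0%) |

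The error rate therefore depends on which reading is adopted. Leaving out the baseline value does not raise it.

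**The case against.** A reader might infer that the plan feeds all three draws into an ordinary regression and so produces false positives. The documents do not say that. A separate model per visit, a change score and a linear mixed model would all fit the words used. A single-visit analysis holds its 5% level, and a naive treatment-by-time contrast is conservative. This part of the objection stands, so the inflated error rates are conditional on one reading.

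Baseline may also have been meant to enter through the outcome. The hypothesis is about rises and falls, the Figure 2 legend reports the group's phase I gene-expression results as fold change from baseline, and log2 suits fold changes. That reading is plausible, but it is not written down. It also does not remove the point: a change score recovers most of the gain at correlation 0.7 (79% against 85%), none at 0.5, and does worse than the raw value at 0.3 (44% against 58%).

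The size of the gain rests on assumed inputs and is small at the low end, 4 points at correlation 0.3. Finally, this is one of several secondary objectives in a phase II trial. Both remarks are correct and limit the weight of the point. They do not argue against the change, since baseline adjustment has the highest power of the three single-visit analyses at every correlation examined and uses a sample already planned.

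**Conclusion.** The concern holds as a missed improvement and a gap in specification. The covariate list is explicit and omits the patient's own baseline biomarker value. Under the assumed 0.5 SD difference with 38 per arm, including it raises power by 4, 12 or 28 percentage points at correlation 0.3, 0.5 or 0.7. The outcome, the visit and the treatment of within-patient correlation are not stated.

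The documents do not support a claim that the plan inflates type I error. That would follow only from pooling draws as independent and testing the treatment main effect, with true rates of about 9% to 13% for the two post-baseline draws or 12% to 21% for all three. The text neither prescribes this nor rules it out. The point is confined to a secondary objective; PFS-1 and its sample size are not touched.

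**What to change.** In Section 10.0 and in the synopsis:

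- Define the outcome of the treatment comparison as the log2 biomarker value at pre-cycle 2.
- Fit a linear model with treatment, the patient's own log2 baseline value and K-RAS, the stratification factor named in Section 5.0. Age, sex and race may stay.
- State that draws from the same patient will not be pooled as independent observations.
- Analyse the off-treatment draw separately and descriptively. It is taken when treatment ends, so its timing depends on outcome and it should not be treated as a common follow-up visit.

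The cost is wording only. The baseline and pre-cycle 2 samples are already in the schedule, and no extra patients, visits or assays are needed.

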12.0 Appendices

- 12.1 RECIST 1.1 criteria for Measurement of Effect
- 12.2 ECOG Performance Status
- 12.3 Handout for patients randomized to the regorafenib arm

12.1 RECIST 1.1 criteria for Measurement of Effect

For the purposes of this study, patients should be re-evaluated for response every **8** weeks.

Definitions

Response and progression will be evaluated in this study using the new international criteria proposed by the Response Evaluation Criteria in Solid Tumors (RECIST) Committee. Changes in only the largest diameter (unidimensional measurement) of the tumor lesions are used in the RECIST criteria (73). Note: Lesions are either measurable or non-measurable using the criteria provided below. The term "evaluable" in reference to measurability will not be used because it does not provide additional meaning or accuracy.

Measurable disease

Measurable lesions are defined as those that can be accurately measured in at least one dimension (longest diameter to be recorded) as > 20 mm with conventional techniques (CT, MRI, x-ray) or as > 10 mm with spiral CT scan. All tumor measurements must be recorded in millimeters (or decimal fractions of centimeters).

Non-measurable disease

All other lesions (or sites of disease), including small lesions (longest diameter < 20 mm with conventional techniques or < 10 mm using spiral CT scan), are considered nonmeasurable disease. Bone lesions, leptomeningeal disease, ascites, pleural/pericardial effusions, lymphangitis cutis, inflammatory breast disease, abdominal masses (not followed by CT or MRI), and cystic lesions are all non-measurable.

Target lesions

All measurable lesions up to a maximum of five lesions per organ and 10 lesions in total, representative of all involved organs, should be identified as target lesions and recorded and measured at baseline. Target lesions should be selected on the basis of their size (lesions with the longest diameter) and their suitability for accurate repeated measurements (either by imaging techniques or clinically). A sum of the longest diameter (LD) for all target lesions will be

calculated and reported as the baseline sum LD. The baseline sum LD will be used as reference by which to characterize the objective tumor response.

Non-target lesions

All other lesions (or sites of disease) should be identified as non-target lesions and should also be recorded at baseline. Non-target lesions include measurable lesions that exceed the maximum numbers per organ or total of all involved organs as well as nonmeasurable lesions.

Measurements of these lesions are not required, but the presence or absence of each should be noted throughout follow-up.

Guidelines for Evaluation of Measurable Disease

All measurements should be taken and recorded in metric notation using a ruler or calipers. All baseline evaluations should be performed as closely as possible to the beginning of treatment and never more than 4 weeks before the beginning of the treatment.

Note: Tumor lesions that are situated in a previously irradiated area are not to be considered evaluable for response, unless documented progression prior to study enrollment.

The same method of assessment and the same technique should be used to characterize each identified and reported lesion at baseline and during follow-up. Imaging-based evaluation is preferred to evaluation by clinical examination when both methods have been used to assess the antitumor effect of a treatment.

Clinical lesions: Clinical lesions will only be considered measurable when they are superficial (e.g., skin nodules and palpable lymph nodes). In the case of skin lesions, documentation by color photography, including a ruler to estimate the size of the lesion, is recommended.

Conventional CT and MRI: These techniques should be performed with cuts of 10 mm or less in slice thickness contiguously. Spiral CT should be performed using a 5 mm contiguous reconstruction algorithm. This applies to tumors of the chest, abdomen, and pelvis. Head and neck tumors and those of extremities usually require specific protocols.

Ultrasound (US): When the primary endpoint of the study is PFS evaluation, US should not be used to measure tumor lesions. It is, however, a possible alternative to clinical measurements of superficial palpable lymph nodes, subcutaneous lesions, and thyroid nodules. US might also be useful to confirm the complete disappearance of superficial lesions usually assessed by clinical examination.

Endoscopy, Laparoscopy: The utilization of these techniques for objective tumor evaluation has not yet been fully and widely validated. Their uses in this specific context require sophisticated equipment and a high level of expertise that may only be available in some centers. Therefore, the utilization of such techniques for objective tumor response should be restricted to validation

purposes in reference centers. However, such techniques may be useful to confirm complete pathological response when biopsies are obtained.

Cytology, Histology: These techniques can be used to differentiate between partial responses (PR) and complete responses (CR) in rare cases (e.g., residual lesions in tumor types, such as germ cell tumors, where known residual benign tumors can remain). *The cytological confirmation of the neoplastic origin of any effusion that appears or worsens during treatment when the measurable tumor has met criteria for response or stable disease is mandatory to differentiate between response or stable disease (an effusion may be a side effect of the treatment) and progressive disease.*

Response Criteria

Evaluation of target lesions

- Complete Response (CR): Disappearance of all target lesions
- Partial Response (PR): At least a 30% decrease in the sum of the longest diameter (LD) of target lesions, taking as reference the baseline sum LD
- Progressive Disease (PD): At least a 20% increase in the sum of the longest diameter (LD) of target lesions, taking as reference the smallest sum LD recorded since treatment started or the appearance of one or more new lesions.
- Stable Disease (SD): Neither sufficient shrinkage to qualify for a PR nor sufficient increase to qualify for PD, taking as reference the smallest sum LD since the treatment started.

Evaluation of non-target lesions

- Complete Response (CR): Disappearance of all non-target lesions and normalization of tumor marker level
- Incomplete Response/ Stable Disease (SD): Persistence of one or more non-target lesions(s) and/or maintenance of tumor marker level above the normal limits.
- Progressive Disease (PD): Appearance of one or more new lesions and/or unequivocal progression of existing non-target lesions.

12.2 ECOG Performance Status

Grade	ECOG
0	Fully active, able to carry on all pre-disease performance without restriction
1	Restricted in physically strenuous activity but ambulatory and able to carry out work of a light or sedentary nature, e.g., light house work, office work
2	Ambulatory and capable of all selfcare but unable to carry out any work activities. Up and about more than 50% of waking hours

3	Capable of only limited selfcare, confined to bed or chair more than 50% of waking hours
4	Completely disabled. Cannot carry on any selfcare. Totally confined to bed or chair
5	Dead

